9.2.2.2. Pharmacokinetics

Analyses Pharmacokinetic

Parameters

Plasma Concentration Summary

Presentations for plasma drug concentrations will include:

- a listing of all concentrations sorted by dose level, subject ID, cycle, day, and nominal time. The concentration listing will also include the actual times. Deviations from the nominal time will be given in a separate listing.

- median concentrations versus nominal time plots (on both linear and semi-log scales) for a dose interval after the morning dose on Cycle 1 Day 1 and Cycle 1 Day 15, separately, by dose level (all treatments on the same plot per scale, based on the stratification of concentrations by dose level and time).

- mean concentrations versus nominal time plots (on both linear and semi-log scales) for a dose interval after the morning dose on Cycle 1 Day 1 and Cycle 1 Day 15, separately, by dose level (all treatments on the same plot per scale, based on the summary of concentrations by dose level and time).

- median concentrations versus nominal time plots (on both linear and semi-log scales) after single dose on Cycle 1 Day -7, Cycle 1 Day -4 and Cycle 1 Day 1 (Pain IC MR Selection Cohort).

- mean concentrations versus nominal time plots (on both linear and semi-log scales) after single dose on Cycle 1 Day -7, Cycle 1 Day -4 and Cycle 1 Day 1 (Pain IC MR Selection Cohort).

Plasma drug concentration time data within a dose interval after the morning dose on Cycle 1, Day 1 (for all patients), Cycle 1, Day 15 (for all patients except Pain IC MR Selection Cohort) and Cycle 1 Day -7/-4 (Pain IC MR Selection Cohort) will be analysed for individual patients using noncompartmental methods. The noncompartmental analysis will estimate PK parameters including the following:

1. Cycle 1, Day 1: the maximal concentration (C_{max}), time to maximum plasma concentration (T_{max}), and area under the plasma concentration versus time curve from time 0 to the last sampling time point within the dose interval (AUC_{last}), and if data permit, area under the plasma concentration versus time curve from time 0 extrapolated to infinity (AUC_{inf}), terminal elimination half life ($t_{1/2}$), apparent oral plasma clearance (CL/F), apparent volume of distribution (V_z/F);
2. Cycle 1, Day 15: steady state C_{max} ($C_{max,ss}$), T_{max} , AUC within one dose interval ($AUC_{r,ss}$), minimum plasma concentration ($C_{min,ss}$), oral CL (CL_{ss}/F), and if data permit, apparent volume of distribution (V_{ss}/F), $t_{1/2}$, and accumulation ratio (R_{ac});
3. Cycle 1, Day -7/-4: the maximal concentration (C_{max}), time to maximum plasma concentration (T_{max}), and area under the plasma concentration versus time curve from time 0 to the last sampling time point within the dose interval (AUC_{last}), and if data permit, area under the plasma concentration versus time curve from time 0 extrapolated to infinity (AUC_{inf}), terminal elimination half life ($t_{1/2}$), apparent oral plasma clearance (CL/F), apparent volume of distribution (V_z/F).

PK parameters will be calculated from the PK concentration-time data using standard non-compartmental methods:

Parameter	Method of Determination
C _∞ , C _{max} ss, C _n ss	Observed directly from data
AUC _{1st} , AUC _{ss}	Linear/log trapezoidal method
AUC _{int}	AUC _{1st} + (C _{1st} *t _{ke1}), where C _{1st} * is the predicted concentration at the last quantifiable time point estimated from the log-linear regression analysis, and ke1 is the terminal phase rate constant calculated by a linear regression of the log-linear concentration-time curve. For the determination of ke1, only those data values that are consistent with the terminal log-linear phase of the log transformed concentration-time curve will be included. The terminal log-linear phase will be determined from a minimum of 3 concentration-time data points, and will be verified with the r ² value.
T _{max}	Observed directly from data.
CL _{IP}	Dose / AUC _{inf}
CL _{ssIF}	Dose / AUC _{ss}
t _{1/2}	ln2/ke1
V _{JP}	Dose / (AUC _{inf} * ke1)
V _p	Dose / (AUC _{inf} * k ₁)
Rae	AUC _{inf} / AUC _{1st}

• if data permut

The actual time of sample collection will be used in PK parameter calculation. In the event that the actual sampling time is not available, the nominal time may be used if there is no evidence that the actual sampling time deviates substantially from the nominal time.

The single dose and steady state PK parameters will be summarized descriptively (n, mean, standard deviation, CV, median, minimum, maximum, geometric mean and its associated CV) by dose, cycle and day.

Pharmacokinetic/Pharmacodynamic (PK/PD) Correlation

PK and PD data from this study may be analyzed using modeling approaches and may also be pooled with data from other studies to investigate any association between PF-06873600 exposure and biomarkers or significant safety endpoints. The results of these analyses, if performed, may be reported separately.

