- a. Pre-dose sample collection:
 - Lead-in, Day-7 and Day-4: within 6 hours prior to the morning dose of PF-06873600;
 - Cycle 1, Day 1: within 6 hours prior to the morning dose of PF-06873600;
 - Cycle 1, Day 8, Day 15 and Day 1 of subsequent cycles: within 30 min prior to the morning dose of PF-06873600.
- b. Prior to the evening dose for BID regimen.
- c. **Pharmacokinetics (PK):** Blood samples of 3 mL each (to obtain at least 1 mL of plasma) for determination of plasma PF-06873600 drug concentrations will be collected at the time points above (NOTE: PK sampling time points may change, pending PK data from early dose levels). Additional PK blood samples may be collected at time of occurrence of unexpected or serious adverse events. On days when patients require predose PK sampling assessments, the morning dose of PF-06873600 should be held (NOT taken) prior to the study visit. On those days, the PF-06873600 morning dose can then be taken after the predose PK sampling is obtained.

d. CCI

I

SCHEDULE OF PHARMACOKINETIC, BIOPSY AND BIOMARKER ASSESSMENTS - IMMEDIATE RELEASE FORMULATION IN PART 2 (ARMS A, BAND C)

	Screening	Cycle											Cycle		EOT
		Day1					Day8	Day15					Day1		
Hours Post-Dose**	O*	1	2	4	6	O*	O*	1	2	4	6	O*	4		
Visit Window†		±6min	±15 min	±25 min	±40 min			±6min	±15 min	±25 min	±40 min		±60 min		
PF-06873600 PK blood sampling ^b	X	X	X	X	X	X	X	X	X	X	X	X			
Food/Dialy	X					X		X				X			
	I												I		
	■												■		
Blood Sample for Circulating	X						X								
	■														
	I														

Abbreviation: CNA = circulating nucleic acid; PK= pharmacokinetic; EOT = End of Treatment; (X) = optional.

Collection Time: Sampling times are related to the **morning dose.

†Sample collection windows: All other sampling should be within the protocol specified window in the table above.

Details for handling of all specimens including processing, storage, and shipment, will be provided in the Laboratory Manual.

a. Pre-dose sample collection:

- Cycle I, Day 1: within 6 hours prior to the morning dose of PF-06873600);
- Cycle I, Day 8, Day 15 and Day 1 of subsequent cycles: within 30 min prior to the morning dose of PF-06873600.

b. **Pharmacokinetics (PK):** Blood samples of 3 mL each (to obtain at least 1 mL of plasma) for determination of plasma PF-06873600 drug concentrations may be collected at time of occurrence of unexpected or serious adverse events.

		Cycle1						Cycle				EOT			
		Day1				Day8		Day15				Day1			

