3.1.3. Part 1C PF06873600 MR Formulation

“A MR formulation with two designed release rates shorter duration (eg, 6 -hour) and longer duration (eg, 12-hour) release, respectively, has been developed for PF-06873600 and were studied in the Part 1C MR Selection Cohort only.” Compared to the Immediate Release (IR) formulation, the MR formulation has the potential to achieve more prolonged effective target inhibition during a dose interval. Emerging pharmacokinetics and safety data for the IR formulation suggest there is a large peak-to-trough fluctuation in steady-state concentrations and that a lower maximal concentration (C_{max}) could potentially improve tolerability. Therefore, the MR formulation with the two release rates were evaluated in an MR selection cohort in this study.

The MR selection cohort enrolled 3 to 5 evaluable patients. These patients received two single doses of the MR formulation during a 7-day lead-in period (Day -7 to Day -1), prior to receiving the IR formulation of PF-06873600 twice daily in 28-day cycles. During the 7-day lead-in period, patients first received a single dose of the shorter release tablets on Day -7, and then another single dose of the longer release tablets on Day -4. The dose for the shorter and longer release MR tablets were administered during the lead-in period, as well as the IR dose administered starting from Cycle 1 Day 1, were no higher than the highest nominal dose tested found to be safe from the IR dose escalation. Serial PK sampling was performed for 24 hours following each of the MR formulation doses on Day -7 and Day -4, and for 12 hours following the IR formulation morning dose on Cycle 1 Day 1. PK was compared between the shorter and longer release MR tablets, and also between each of the two release rate MR tablets and IR. Based on the PK data from the MR selection cohort, 12-hour release rate provides a slower release compared to the 6-hour release rate, thus achieves more prolonged drug coverage during a dosing interval. Therefore, 12-hour release rate was selected to be further investigated during MR dose escalation.

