9.5. Analysis of Pharmacokinetics and Pharmacodynamics

9.5.1. Analysis of Pharmacokinetics

9.5.1.1. Single-Dose and Steady-State PF-06873600 Pharmacokinetic Analysis

Plasma concentrations of PF-06873600 will be summarized descriptively (n, mean, standard deviation, CV, median, minimum, maximum, geometric mean and its associated CV) by dose, cycle, day, and nominal time.

Plasma concentration-time data within a dose interval after the morning dose on Cycle 1, Day 1 (for patients of Part 1A and 1B), Cycle 1, Day 15 (for all patients, with exception of the MR formulation selection cohort) or for patients of the MR formulation selection cohort, plasma concentration-time data after Day -7 and Day -4, respectively, will be analysed for individual patients using noncompartmental methods. The noncompartmental analysis will estimate PK parameters including the following:

1. Cycle 1 Day 1 (and also Lead-in Day -7 and Day -4 for patients of the MR formulation selection cohort within Part 1C): the maximal concentration (C_{max}), time to maximum plasma concentration (T_{max}), and area under the plasma concentration versus time curve from time 0 to the last sampling time point within the dose interval (AUC_{last}), and if data permit, area under the plasma concentration versus time curve from time 0 extrapolated to infinity (AUC_{inf}), terminal elimination half-life ($t_{1/2}$), apparent oral plasma clearance (CL/F), apparent volume of distribution (V_z/F);
2. Cycle 1 Day 15: steady state C_{max} ($C_{max,ss}$), T_{max} , AUC within one dose interval ($AUC_{\tau,ss}$), minimum plasma concentration ($C_{min,ss}$), oral CL (CL_{ss}/F), and if data permit, apparent volume of distribution (V_{ss}/F), $t_{1/2}$, and accumulation ratio (R_{ac}).

The single-dose and steady-state PK parameters will be summarized descriptively (n, mean, standard deviation, coefficient of variation (CV), median, minimum, maximum, geometric mean and its associated CV) by dose, cycle and day.

Dose normalized AUC_{inf} (AUC_{τ} at steady state), AUC_{last} and C_{max} will be plotted against dose (using a logarithmic scale) by cycle and day. These plots will include individual patient values and the geometric means for each dose. These plots will be used to help understand the relationship between the PK parameters and dose.

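### SAP 9.2.2.2 applies AUClast, AUCtau,ss and CLss/F to Part 2 IR patients sampled for only 6 h of a 12 h interval, and summary rows by dose, cycle and day mix those areas with Part 1's 12 h areas

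*SAP*

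**What the plan says.** **Scope.** SAP 9.2.2.2 analyses plasma data "within a dose interval after the morning dose on Cycle 1, Day 1 (for all patients), Cycle 1, Day 15 (for all patients except" the MR selection cohort in Part 1C. Protocol 9.5.1.1 is narrower on Day 1 but equally broad on Day 15: "for patients of Part 1A and 1B), Cycle 1, Day 15 (for all patients, with exception of the MR formulation selection cohort". 

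**Parameters.** On Day 1, AUClast runs from "time 0 to the last sampling time point within the dose interval". On Day 15, AUCtau,ss and CLss/F are listed by the linear/log trapezoidal method. These three carry no condition. AUCinf, half-life, CL/F, Vz/F, Vss/F and Rac are to be given only where the data allow.

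**Summaries.** "The single dose and steady state PK parameters will be summarized descriptively" by dose, cycle and day. Formulation, study part and combination partner are not strata.

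**Sampling (protocol PK schedules).**
- Part 1 BID and the Japan lead-in cohort: to 12 h on Days 1 and 15.
- Part 2 IR: 0, 1, 2, 4 and 6 h on Days 1 and 15.
- Part 2 MR: to 12 h on both days.
- MR selection cohort: 24 h after each lead-in MR dose and 12 h after the IR dose on Cycle 1 Day 1 (protocol 3.1.3).

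The BID interval is 12 h (protocol 5.4.1).

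**Part 2 endpoints.** SAP 2.3 lists Cmax and Tmax for single dose, and Css,max, Tss,max, Css,min and an accumulation ratio on Cmax for multiple dose. It lists no AUC and no clearance.

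**The concern.** AUClast means whatever window was sampled. Where two groups at one dose stop at different times, an AUClast row averages two different quantities. The design makes shared doses likely. Part 1B starts at the single-agent MTD/RDE (protocol 3.1), Part 2 starts at the Part 1B RDE (protocol 3.2), and Part 1B enrols at least 6 patients at each combination's RDE (protocol 3.1.2).

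Nothing in the SAP catches this. Section 8.3 codes a parameter as not calculated when it cannot be derived, but AUClast can always be computed from a 0-6 h profile. On Day 15 the analyst has no rule for 6 to 12 h and must choose between a missing value, an extrapolation, the pre-dose value or the 6 h area. At stake is whether the reported AUC and clearance at the expansion dose reflect exposure or the time at which sampling stopped.

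**Working it through.** **The plan's own figure.** Protocol 1.3.2 predicts CL 1.0 mL/min/kg, Vss 0.8 L/kg, F about 40% and a half-life of about 9 h.
- Half-life = ln 2 × V/CL = 0.693 × 800/1.0 = 554.5 min = 9.24 h.
- CL/F = 1.0/0.4 = 2.5 mL/min/kg; V/F = 0.8/0.4 = 2 L/kg. All reproduce.

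**Assumptions.** One compartment with first-order absorption, ka = 1.5/h. Half-life is the predicted 9 h, with 3 h as the assumed lower end, because the documents give no observed human value.

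**Single dose.** The fraction of AUCinf collected by time t is

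f(t) = 1 − (ka·e^(−kt) − k·e^(−ka·t))/(ka − k).

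- Half-life 9 h, k = 0.0770: f(6) = 1 − (1.5 × 0.6300)/1.423 = 0.336; f(12) = 1 − (1.5 × 0.3969)/1.423 = 0.582. Ratio 0.336/0.582 = **0.58**.
- Half-life 3 h, k = 0.2310: f(6) = 1 − (1.5 × 0.2500)/1.269 = 0.705; f(12) = 1 − (1.5 × 0.0625)/1.269 = 0.926. Ratio 0.705/0.926 = **0.76**.

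(The k·e^(−ka·t) term is negligible here.) Setting ka from Tmax of 0.5 to 4 h, the preclinical range in protocol 1.3.2, and half-life from 3 to 9.24 h widens the ratio to 0.51-0.79.

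**Effect on a mixed row.** If a share p of the row is Part 2 IR, the mean is 1 − p(1 − ratio) of the pure 0-12 h mean. For an illustrative p of 0.5 this is 1 − 0.5 × 0.42 = 0.79 at 9 h and 1 − 0.5 × 0.24 = 0.88 at 3 h. The actual p is not in the documents.

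**Steady state.** In the same model with a 12 h interval, AUC0-6/AUC0-12 is 0.59 at 9 h and 0.76 at 3 h. If the 6 h area were reported as AUCtau,ss, CLss/F would be overstated by 1/0.59 = 1.69 times (1/0.76 = 1.31 at 3 h).

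**Whether AUCtau,ss can be recovered.** Under BID steady state the 12 h concentration equals the Day 15 pre-dose value, which is sampled. Adding it as a 12 h point to the 0, 1, 2, 4, 6 h grid and applying the linear/log trapezoidal rule gives 97% (3 h) to 99% (9 h) of the true AUCtau,ss. Over the wider Tmax range it gives 92-99%.

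**MR lead-in against IR.** Assume equal total exposure and 12 h zero-order release. The MR fraction to 12 h is (12 − (1 − e^(−12k))/k)/12, which at 9 h is (12 − 7.83)/12 = 0.347. From 12 to 24 h it adds (1 − e^(−12k))²/(12k) = 0.364/0.924 = 0.394, so the 0-24 h fraction is 0.741.
- MR 0-24 h over IR 0-12 h = 0.741/0.582 = 1.27 (1.06 at 3 h).
- MR 0-12 h over IR 0-12 h = 0.347/0.582 = 0.60.

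**The case against.** Much of the case on the other side stands.

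- A reader might infer that the SAP demands the full parameter set in everyone. It does not. AUCinf, half-life, CL/F, the volumes and Rac are conditional, and terminal-phase estimates are limited to data consistent with the log-linear phase as well as "determined from a minimum of 3 concentration-time data points".
- A reader might infer that AUCtau,ss is beyond reach in Part 2 IR. It is not: the Day 15 pre-dose value recovers nearly all of it. The SAP does not prespecify that step, and its written fallback in 8.3 is a missing value, not a 6 h area passed off as AUCtau,ss.
- A reader might infer that the tables will show lower exposure in Part 2 than in Part 1 and suggest an interaction. A pooled row cannot show a between-part difference. Single agent and combination can also be compared within Part 1, where both are sampled to 12 h.
- A reader might infer that MR will look more bioavailable than IR. "Serial PK sampling was performed for 24 hours following each of the MR formulation doses on Day -7 and Day -4, and for 12 hours" after IR, so the windows do differ. But the 24 h profiles fall on separate days and are not pooled with Day 1, the SAP plans no MR/IR AUC ratio, and the release rate has already been chosen.
- AUC is not a listed Part 2 endpoint, although the protocol's list is expressly not exhaustive. The current IR schedule keeps PK samples only at adverse events, so only patients profiled earlier are affected.
- The protocol reports large peak-to-trough fluctuation for IR, which points to a half-life shorter than 9 h and so to the milder end of the range.

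None of this removes the mixed AUClast row, the missing rule for 6 to 12 h, or the conflicts over scope.

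**Conclusion.** The point holds in limited form. SAP 9.2.2.2 asks for AUClast, AUCtau,ss and CLss/F in Part 2 IR patients whose scheduled profiles end halfway through the dosing interval. Its strata allow their 0-6 h AUClast to be averaged with 0-12 h values at the same dose. The 6 h area is about 58% of the 12 h area at the predicted 9 h half-life and 76% at 3 h. These figures rest on an assumed one-compartment model and predicted PK, so they give direction and rough size only.

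On Day 1 the SAP is wider than protocol 9.5.1.1. On Day 15 both documents include Part 2. The SAP's own Part 2 list contains neither AUC nor clearance. The practical effect also assumes that some Part 2 patients received IR and had scheduled profiles; the documents do not say how many. No hypothesis test or dosing rule depends on these summaries. The documents do not support a claim of a spurious interaction or of a planned biased MR/IR bioavailability estimate.

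**What to change.** In SAP 9.2.2.2:

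1. Limit Part 2 IR to the parameters in SAP 2.3. Alternatively, report AUC0-6 under that name, and derive AUCtau,ss and CLss/F only with the Day 15 pre-dose value used as the 12 h concentration. Part 2 MR, sampled to 12 h, can keep AUCtau,ss.
2. Align the Day 1 scope for area-based parameters with protocol 9.5.1.1. Keep Cmax and Tmax for Part 2, which SAP 2.3 lists. State explicitly that Part 1C stays in: the protocol sentence does not name it for Day 1, but it is sampled to 12 h and its single-dose PK is a Part 1 objective.
3. Summarise PK parameters by formulation and by study part or combination partner, as well as dose, cycle and day.
4. If MR lead-in AUC is set against IR Day 1 AUC in the report, use a common 0-12 h window, the longest one sampled for both. Label it as exposure over one dosing interval. It is not relative bioavailability, since it reads 0.60 in the model above even at equal total exposure.

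The cost is SAP wording and programming; no new samples are needed. Fewer patients contribute AUC and clearance summaries, and there are more and smaller summary rows.

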9.2.2.3. Biomarker Analyses

Level of pharmacodynamic (PD) markers, pRb and Ki67 from each dose will be analyzed at two time points, at screening and at cycle 2 day 1 of each patient. Percent changes of biomarkers at Cycle 2 Day 1 from Screening (baseline) will be calculated and summarized; actual biomarker levels will be listed by visit.

Summary statistics for percentage change from baseline of biomarker level may include geometric mean, 95% confidence interval, median, and minimum/maximum. Other exploratory biomarkers analyzed with the remaining tumor specimens will be described in the biomarker Statistical Analysis Plan (bSAP).

9.2.3. Safety Analyses

9.2.3.1. Adverse Events

Adverse Events (Aes) will be graded by the investigator according to the CTCAE version 4.03 and coded using the Med.ORA. The focus of AE summaries will be on Treatment Emergent Adverse Events, those with initial onset or increasing in severity after the first dose of study treatment. The number and percentage of patients who experienced any AE, serious AE (SAE), treatment related AE, treatment related SAE, and any AEs leading to dose interruptions, dose reductions, drug discontinuations, and/or death will be summarized according to worst toxicity grades. The summaries will present AEs based on the entire study period (all cycles). The Safety Analysis Set will be used.

9.2.3.2. Laboratory Tests Abnormalities

The number and percentage of patients who experienced laboratory test abnormalities will be summarized according to worst toxicity grade observed for each laboratory test. The analyses will summarize laboratory tests based on the entire study period (all cycles). Shift tables will be provided to examine the distribution of laboratory abnormalities, and worst on-study abnormalities will be summarized. The Safety Analysis Set will be used.

For laboratory tests without CTC grade definitions, results will be categorized as normal, abnormal high/low or not done.

